These calculations are carried out assuming 5% annual dropout, 5% probability of missing any of the 3 doses, VE(COVID) of 63% between Month 0 and Month 6 in Group 1 (SARs-CoV-2 negative) and in Group 2, and 5% six-month COVID-19 incidence rate among unvaccinated PLWH SARs-CoV-2 negative individuals in the community. The assumption on VE(COVID) of 63% between Month 0 and Month 6 accounts for a possible reduced protection of the vaccine regimen in PLWH against the SARS-CoV-2 variant at the time of the trial conduct. The 5% six-month background incidence rate assumption was based on the observed 4.7%, 5.25%, and 10.38% placebo arm six-month incidence rates among baseline SARS-CoV-2 negative participants in, respectively, the AstraZeneca phase 3 (149), Novavax phase 2 (107), and Janssen ENSEMBLE phase 3 (28) trials restricted to South African study sites, and building in conservative margin given the availability of vaccines to potentially reduce transmission and infection in the region. The background SARS-CoV-2 (re-infection) incidence rate among unvaccinated PLWH SARS-CoV-2 positive individuals in the community is assumed to be half of that of unvaccinated PLWH SARS-CoV-2 negative individuals based on the reported protection of approximately 55% against the Omicron variant from previous SARS-CoV-2 infection in South Africa (150-152) and in other countries (153). The statistical power is calculated using an exact binomial test with a (two-sided) false positive error rate of 0.05.

**Table 6-2 Pre-Month 6 stage:** power to detect relative risk (Months 0-6) being different from 1.0 between Group 1 (n=4200) and Group 2 (n=8400).

True VE (0-6) of Group 1 (n=4200)	Relative Risk (Groups 1 vs. 2)	Total expected number of events M0-6	Power
60%	1.3	189	45%
	1.6	176	85%
	2.0	167	99%
70%	1.2	149	17%
	1.5	135	59%
	2.0	125	96%
70%	1/1.3	207	45%
75%	1/1.6	203	85%
80%	1/2.0	200	99%
75%	1/1.2	159	17%
80%	1/1.5	153	59%
85%	1/2.0	150	96%

**Post-Month 6 stage:** power to detect relative risk (Months 6.5-18) being different from 1.0 between mRNA-1273 vs. mRNA-1273.222 Month 6 vaccination (n=4000, 2000 vs. 2000),.

Annual incidence for mRNA-1273 Month 6 vaccination arm	Relative Risk (mRNA-1273 vs. mRNA-1273.222)	Total expected number of events M6.5-18	Power
3.5%	1.5	110	54%
	2.0	106	93%
3.0%	2.0	91	87%
	2.5	90	99%
2.5%	2.0	76	78%
	2.5	75	96%

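### The expected event totals in the pre-Month 6 panel of Table 6-2 cannot all come from one set of the stated inputs, and the rows labelled RR 1.3 carry the power for RR 4/3

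*Protocol*

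**What the plan says.** Protocol Section 6.3.1 gives these inputs for the Group 1 versus Group 2 comparison over Months 0 to 6:

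- Background risk: a "5% six-month COVID-19 incidence rate among unvaccinated PLWH" without prior infection. The background in previously infected PLWH "is assumed to be half of that of unvaccinated PLWH SARS-CoV-2 negative individuals".
- Vaccine effect: "VE(COVID) of 63% between Month 0 and Month 6 in Group 1", with the same figure for Group 2.
- Attrition: "5% annual dropout, 5% probability of missing any of the 3 doses".
- Test: "The statistical power is calculated using an exact binomial test with a (two-sided) false positive error rate of 0.05".

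The pre-Month 6 panel of Table 6-2 then prints twelve rows, each with a Group 1 VE (60% to 85%), an RR, a total expected number of events and a power. The section says that the panel uses the FAS sizes of Groups 1 and 2. It draws one conclusion from it: power exceeds 90% at RR 2.0. It does not say how dropout or missed doses change the event totals.

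**The concern.** Once group sizes, background risk and Group 1 VE are fixed, expected Group 1 events are fixed too. Changing the RR can change only the Group 2 events. The printed totals break this rule. In addition, the 45% power in the two rows labelled 1.3 is not what the stated test gives at 1.3.

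Section 6.3 says that the sizes of Groups 1 and 2 are driven by the number of COVID-19 cases needed, and this panel is the protocol's only power calculation for the pre-Month 6 efficacy comparison. A reader should be able to regenerate it. At stake is the accuracy of the stated event counts, and of the stated sensitivity to effects smaller than RR 2.0.

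**Working it through.** **Inputs** (Section 6.3.1 and Table 6-2): n1 = 4,200, n2 = 8,400, background 5%, VE and RR by row, two-sided 0.05 exact binomial test.

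**Formulas.** Group 1 events before attrition: E1 = 4,200 × 0.05 × (1 − VE). Total: D = E1 × (1 + 2/RR), because Group 2 is twice as large and has risk 1/RR times that of Group 1. Power: given D, Group 1 events are binomial with share p0 = 4,200/12,600 = 1/3 under the null and p1 = RR/(RR + 2) under the alternative, with equal tails.

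**Step 1: reproduce the printed powers from the printed totals.** All twelve agree within about 1 point if the 1.3 rows are 4/3 and 3/4.

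| Group 1 VE | RR | Printed D | D before attrition | Ratio | Implied E1 = printed D/(1 + 2/RR) | Printed power | Power at printed D |
|---|---|---|---|---|---|---|---|
| 60% | 4/3 | 189 | 210 | 0.900 | 75.6 | 45% | 44.5% |
| 60% | 1.6 | 176 | 189 | 0.931 | 78.2 | 85% | 84.6% |
| 60% | 2.0 | 167 | 168 | 0.994 | 83.5 | 99% | 99.0% |
| 70% | 1.2 | 149 | 168 | 0.887 | 55.9 | 17% | 17.2% |
| 70% | 1.5 | 135 | 147 | 0.918 | 57.9 | 59% | 59.2% |
| 70% | 2.0 | 125 | 126 | 0.992 | 62.5 | 96% | 96.3% |
| 70% | 3/4 | 207 | 231 | 0.896 | 56.5 | 45% | 44.5% |
| 75% | 1/1.6 | 203 | 220.5 | 0.921 | 48.3 | 85% | 84.5% |
| 80% | 1/2.0 | 200 | 210 | 0.952 | 40.0 | 99% | 99.0% |
| 75% | 1/1.2 | 159 | 178.5 | 0.891 | 46.8 | 17% | 18.1% |
| 80% | 1/1.5 | 153 | 168 | 0.911 | 38.2 | 59% | 59.8% |
| 85% | 1/2.0 | 150 | 157.5 | 0.952 | 30.0 | 96% | 95.5% |

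**Step 2: the RR 1.3 label.** At exactly 1.30, power is 37.9% with 189 events and 38.2% with 207, against 45% printed. The rows fit Group 2 VE of 40% and 20% on the 2.5% background: (0.05 × 0.40)/(0.025 × 0.60) = 4/3, and (0.05 × 0.30)/(0.025 × 0.80) = 3/4.

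**Step 3: internal consistency of the totals.** Before attrition, E1 is 84 at VE 60% and 63 at VE 70%. The printed totals imply 75.6, 78.2 and 83.5 in the three VE 60% rows. In the four VE 70% rows they imply 55.9, 57.9, 62.5 and 56.5. The ratio of printed to unattrited totals runs from 0.887 to 0.994, so no single attrition factor yields all twelve.

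**Step 4: how many totals fail**, at a 3% tolerance:

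| Attrition applied to both groups | Factor | Totals reproduced | Totals failing |
|---|---|---|---|
| None | 1 | 2 | 10 |
| Dropout as lost person-time (1.25%) | 0.9875 | 2 | 10 |
| Missed dose plus person-time dropout | 0.95 × 0.9875 = 0.938 | 6 | 6 |
| Missed dose plus full six-month dropout | 0.95 × 0.975 = 0.926 | 7 | 5 |
| Best common factor | about 0.91 | 8 | 4 |

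Separate factors for each group reach at most 10 of 12, and need a 14% loss in Group 1 that the protocol does not state.

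**Step 5: effect on power**, with the 1.3 rows taken as 4/3 and 3/4. With factor 0.938, no row moves by more than 2.4 points (RR 1.2: 19.4% against 17%). With no attrition or 0.9875, most rows move by 0 to 3 points, and three gaps are larger. Each falls at a peak of the exact test's sawtooth:

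- RR 4/3: 51.5% at 207 events, but 47.0% at 205 and at 210 (printed 45%).
- RR 1/1.5: 64.5% at 166 events, but 59.4% at 165 (printed 59%).
- RR 1.5: 66.0% at 147 events, but 60.7% at 145 (printed 59%).

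At RR 2.0 and 1/2.0, power is 94% or more in every attrition variant.

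**Step 6: the base case in the text.** With VE 63% in both groups and half the background in Group 2, each group has 77.7 expected events (4,200 × 0.05 × 0.37 and 8,400 × 0.025 × 0.37). That is RR 2.0 with 155.4 events (about 153 after 1.25% person-time loss) and 98% to 99% power. No row shows it.

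**The case against.** The strongest reply is that nothing rests on the error. The power column agrees with its own event column, 4/3 rounds to 1.3, and the single conclusion at RR 2.0 survives every variant. Section 6.3.1 already warns that the real comparison groups are likely smaller, and Table 1-1 calls the sizes approximate ceilings. Section 2.1 reports interim annual incidence in PLWH of 7.1% against 2.2%, a ratio of about 3.2, so power at RR 1.2 to 1.6 no longer guides a decision. The 63% case lies between the 60% and 70% rows and is favourable. All of this stands, and it makes the point minor.

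Two stronger readings are tempting and are not supported. A reader might infer that ten of the twelve totals are wrong. That count holds only if the stated 5% missed-dose input is left out. There is a case for leaving it out: the FAS needs only one administration, and Section 6.4 analyses participants regardless of the number of vaccinations. But Section 6.4.3 describes the compared groups by the doses they receive, and Section 6.3.1 does not say how the input is used, so the documents fix no count. A reader might also infer that the stated powers are wrong by up to 7 points. That requires reading a one-decimal label as exactly 1.30, or picking totals at a sawtooth peak.

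The reply does not remove the contradiction between rows with the same VE. No common attrition assumption repairs it.

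**Conclusion.** Wrong as written, of minor severity. At least four of the twelve pre-Month 6 totals are inconsistent with the stated inputs under any common attrition factor. Five or six are if missed doses count as losses, and ten if they do not; all these counts use a 3% tolerance. The label 1.3 stands for 4/3, and taking it literally overstates power by about 7 points (45% against 38%). Otherwise the powers match the printed totals, and regenerating the totals moves most of them by about 0 to 3 points. The result does not show that the comparison is underpowered: at the stated group sizes, power at RR 2.0 stays at 94% or more. The check assumes the conditional exact test with equal tails, and group risks that differ only by the row RR.

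**What to change.** In Section 6.3.1, state how 5% annual dropout and the 5% missed-dose probability enter the FAS event totals. Regenerate the pre-Month 6 totals and powers from the stated inputs. Label the affected rows 1.33 and 1/1.33, or recompute them at 1.30. Add a row for the 63% VE base case or delete it from the text. The cost is one recalculated table panel and a sentence or two. Group sizes, follow-up and conduct do not change, and the RR 2.0 statement can stay.

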### 6.3.2 Power calculations for coprimary objective 5 (Safety)

For pre-Month 6 stage, we consider power for evaluating the safety objective using a total of N = 15,600 participants in the Full Analysis Set (FAS) and N = 1,500 in the Safety Subset (SS). If no SAE or AESI that is considered related to the study vaccine is observed in the FAS, or no AE in the SS, the upper limit of the 95% confidence interval (CI) for the true event rate will be 0.02% or 0.2%, respectively. Hence, observing no SAE/AESI in the FAS or no AE in the SS would provide us with 95% confidence that the true event rate is no more than 0.02% or 0.2%, respectively. For post-Month 6 stage, we consider power for evaluating the safety objective of the mRNA-1273 or mRNA-1273.222 vaccination at Month 6 using half of the cohorts assessed for pre-Month 6 stage and additionally assuming 80% of these cohorts receiving the Month 6 vaccination under the current protocol version. [Table 6-4](#) shows the 95% CIs for event rates ranging from 0% to 5% in the full or half of the FAS, FAS.Grp1-4 and SS, demonstrating the degree of precision conferred by the trial size for evaluating safety events in these cohorts. CIs were calculated using the Clopper-Pearson method (154).

**Table 6-4 Pre-Month 6 stage:** Confidence intervals (CIs) for observed safety event rates in the FAS (N = 15,600), FAS.Grp1-4 (N = 4,200, 8,400, 1,000, 2,000) and the SS (N = 1500) cohorts concerning the mRNA-1273 regimen. Confidence intervals were calculated using the Clopper-Pearson method (154).

Safety Event	FAS (N = 15,600)	FAS.Grp1 (N = 4,200)	FAS.Grp2 (N = 8,400)	FAS.Grp3 (N = 1,000)	FAS.Grp4 (N = 2,000)	SS (N = 1,500)
Rate (%)	CI (%)	CI (%)	CI (%)	CI (%)	CI (%)	CI (%)
0.0	(0.0, 0.0)	(0.0, 0.1)	(0.0, 0.0)	(0.0, 0.4)	(0.0, 0.2)	(0.0, 0.2)
0.5	(0.4, 0.6)	(0.3, 0.8)	(0.4, 0.7)	(0.2, 1.2)	(0.2, 0.9)	(0.2, 1.0)
1.0	(0.8, 1.2)	(0.7, 1.3)	(0.8, 1.2)	(0.5, 1.8)	(0.6, 1.5)	(0.6, 1.6)
2.0	(1.8, 2.2)	(1.6, 2.5)	(1.7, 2.3)	(1.2, 3.1)	(1.4, 2.7)	(1.4, 2.8)
3.0	(2.7, 3.3)	(2.5, 3.6)	(2.6, 3.4)	(2.0, 4.3)	(2.2, 3.8)	(2.2, 4.0)
4.0	(3.7, 4.3)	(3.4, 4.6)	(3.6, 4.4)	(2.9, 5.4)	(3.2, 5.0)	(3.1, 5.1)
5.0	(4.7, 5.4)	(4.4, 5.7)	(4.5, 5.5)	(3.7, 6.5)	(4.1, 6.0)	(4.0, 6.2)

**Post-Month 6 stage:** Confidence intervals (CIs) for observed safety event rates in half of the FAS (N = 0.8\*15,600/2), FAS.Grp1-4 (N = 0.8\*4,200/2, 0.8\*8,400/2, 0.8\*1,000/2, 0.8\*2,000/2) and the SS (N = 0.8\*1500/2) cohorts concerning each type of Month 6 vaccination (mRNA-1273 or mRNA-1273.222), assuming 80% of these cohorts receiving the Month 6 vaccination under the current protocol version. Confidence intervals were calculated using the Clopper-Pearson method (154).

Safety Event Rate (%)	N = 6,240	N = 1,680	N = 3,360	N = 400	N = 800	N = 600
0.0	(0.0, 0.1)	(0.0, 0.2)	(0.0, 0.1)	(0.0, 0.9)	(0.0, 0.4)	(0.0, 0.6)
0.5	(0.3, 0.7)	(0.2, 1.0)	(0.3, 0.8)	(0.1, 1.8)	(0.1, 1.3)	(0.1, 1.5)
1.0	(0.8, 1.3)	(0.6, 1.6)	(0.7, 1.4)	(0.3, 2.5)	(0.4, 2.0)	(0.4, 2.2)
2.0	(1.7, 2.4)	(1.4, 2.8)	(1.6, 2.5)	(0.9, 3.9)	(1.1, 3.2)	(1.0, 3.5)
3.0	(2.6, 3.5)	(2.2, 3.9)	(2.5, 3.6)	(1.6, 5.2)	(1.9, 4.4)	(1.8, 4.7)
4.0	(3.5, 4.5)	(1.1, 5.1)	(3.4, 4.7)	(2.3, 6.4)	(2.8, 5.6)	(2.6, 5.9)
5.0	(4.5, 5.6)	(4.0, 6.2)	(4.4, 5.8)	(3.1, 7.6)	(3.6, 6.7)	(3.4, 7.1)

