### 6.3.1 Power calculations for coprimary objectives 1-4 (Efficacy)

Let  $VE(COVID)$  and  $VE(Severe\ COVID)$  denote vaccine efficacy of the vaccine regimen vs. counterfactual placebo among baseline SARS-CoV-2 negative participants against COVID-19 and severe COVID-19, respectively. The relative risk objectives are assessed in terms of cumulative incidence ratios between the active vaccine regimens without analysis of counterfactual placebo arms; the notations  $VE(COVID)$  and  $VE(Severe\ COVID)$  are mainly used for purposes of communicating effect sizes.

The following calculations focus on the COVID-19 endpoint because the severe COVID-19 endpoint could potentially be changed to be a secondary endpoint if there are insufficient severe COVID endpoints (Section 6.4.3). For the assessment of pre-Month 6 stage objectives, sample sizes of Groups 1 and 2 in the FAS are considered. For the assessment of post-Month 6 stage objectives, the following calculations consider approximately 4000 participants in Groups 1-4 received their Month 6 vaccination (mRNA-1273 vs. mRNA-1273.222) per randomization under protocol version 6. This sample size is consistent with study data as of June 2023. As shown in the upper portion (pre-Month 6 stage) of Table 6-2, there is ample power ( $> 90\%$ ) to detect a relative risk of 2.0 between Groups 1 and 2 against the null hypothesis  $H_0: RR = 1.0$  during Month 0 and 6 in the pre-Month 6 stage. In reality, the sample sizes of the PLWH hybrid immunity group who receive 1 pre-Month 6 dose and the PLWH pure vaccine group who receive 2 pre-Month 6 doses are likely smaller than the sample sizes of Groups 1 and 2, respectively. As shown in the lower portion (post-Month 6 stage) of Table 6-2, when the annual incidence of the primary endpoint is in the range of 2.5%- 3.5% in the mRNA-1273 arm, there is approximately 80-90% power to detect a relative risk of 2.0 – 2.5 between mRNA-1273 vs. mRNA-1273.222 vaccination during Month 6.5 and 18 in the post-Month 6 stage.

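### The post-Month 6 panel of Table 6-4 assumes 6,240 recipients per vaccine, but Section 6.3.1 puts the randomised Month 6 group at about 2,000 per arm, so the full-cohort and Group 2 bivalent columns cannot hold

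*Protocol*

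**What the plan says.** **Safety (Protocol Section 6.3.2).** The pre-Month 6 precision starts from 15,600 participants in the Full Analysis Set and 1,500 in the Safety Subset. For the post-Month 6 stage the protocol allots one half of each cohort to each vaccine. It then scales the result down, "additionally assuming 80% of these cohorts receiving the Month 6 vaccination under the current protocol version". The post-Month 6 panel of Table 6-4 then gives exact 95% intervals for N = 6,240 (full cohort), 1,680, 3,360, 400 and 800 (Groups 1 to 4) and 600 (Safety Subset). The panel title says that these are "cohorts concerning each type of Month 6 vaccination (mRNA-1273 or mRNA-1273.222"), so each N is meant to apply to the bivalent vaccine as well as to the monovalent one.

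**Efficacy (Protocol Section 6.3.1).** The post-Month 6 power calculation rests on "approximately 4000 participants in Groups 1-4 received their Month 6 vaccination (mRNA-1273 vs. mRNA-1273.222) per randomization under protocol version 6". The protocol adds: "This sample size is consistent with study data as of June 2023". Table 6-2 splits this as 2,000 vs. 2,000.

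**Who could receive the bivalent vaccine.** SAP Section 2 reports 14,237 enrolled and states that Month 6 doses before version 6.0 were all monovalent, because the bivalent product was not yet available. The Protocol Overview agrees.

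**The concern.** Two adjacent subsections of one protocol version give incompatible sizes for the same dosed population. The efficacy section uses a count tied to study data. The safety section uses a planning fraction of the enrolment ceiling that is about three times as large.

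Safety and tolerability of both vaccines is primary objective 5, and mRNA-1273.222 is the newer product. Section 6.3.2 presents the table as showing what precision the trial size delivers. A reader who relies on it would believe that rare events after bivalent vaccination can be bounded about three times more tightly than the reported numbers allow.

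**Working it through.** **Inputs**

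- Enrolment ceiling 15,600, share dosed 80%, half per vaccine: Protocol Section 6.3.2.
- Version 6 randomised recipients about 4,000, 2,000 per arm: Protocol Section 6.3.1 and Table 6-2.
- Enrolled 14,237: SAP Section 2.
- Interval method: Clopper-Pearson, two-sided 95%. For x events in N, the limits are the 2.5% quantile of Beta(x, N − x + 1) and the 97.5% quantile of Beta(x + 1, N − x). For x = 0 the upper limit is 1 − 0.025^(1/N).

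**Step 1: reproduce the plan's figures.** 0.8 × 15,600 = 12,480, and 12,480 / 2 = 6,240. The whole N = 6,240 column reproduces to one decimal; for example, the zero-event upper limit is 0.059% (printed 0.1) and the interval at 1% is 0.763 to 1.272 (printed 0.8 to 1.3). The method is as stated. What is in question is N.

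**Step 2: compare the two sizes.**

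- 4,000 / 15,600 = 25.6% of the ceiling, and 4,000 / 14,237 = 28.1% of those enrolled, against the assumed 80%.
- 6,240 / 2,000 = 3.1.
- 6,240 per vaccine would need 12,480 / 14,237 = 87.7% of everyone enrolled to be dosed under the randomised scheme.

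**Step 3: recompute the full-cohort column with N = 2,000.**

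| Observed rate | N = 6,240, computed (%) | Printed (%) | N = 2,000 (%) |
|---|---|---|---|
| 0% | 0 to 0.059 | 0.0, 0.1 | 0 to 0.18 |
| 0.5% | 0.338 to 0.704 | 0.3, 0.7 | 0.24 to 0.92 |
| 1% | 0.763 to 1.272 | 0.8, 1.3 | 0.61 to 1.54 |
| 2% | 1.670 to 2.382 | 1.7, 2.4 | 1.43 to 2.71 |
| 5% | 4.472 to 5.570 | 4.5, 5.6 | 4.09 to 6.05 |

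The zero-event limit rises 3.1 times (0.184 / 0.059). At 1% the width goes from 0.509 to 0.928 points, a factor of 1.8. For a true event rate of 0.05%, the chance of seeing at least one event is 1 − 0.9995^6,240 = 95.6% with 6,240 recipients and 1 − 0.9995^2,000 = 63.2% with 2,000.

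**Step 4: which columns fail for the bivalent vaccine.** With about 2,000 recipients, 6,240 and 3,360 each exceed the total and are impossible. Since 1,680 + 3,360 + 400 + 800 = 6,240, the four group columns cannot all be right. Taken singly, 1,680, 400 and 800 are each below 2,000, and so is the Safety Subset's 600.

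**Step 5: sensitivity.** If the bivalent count is 1,500, the zero-event limit is 0.25%; if 2,500, it is 0.15%. The N = 6,240 and N = 3,360 columns fail throughout this range. If version 6 recipients split in proportion to the printed columns (an assumption), the per-vaccine N would be about 538, 1,077, 128 and 256 for Groups 1 to 4 and 192 for the Safety Subset. The zero-event limits would be about 0.7, 0.3, 2.8, 1.4 and 1.9%.

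**Step 6: misprints.** Of the panel's 84 limits, 81 reproduce, allowing the event count to be fractional or rounded either way. The other three are:

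- N = 1,680 at 4%, lower limit: printed 1.1, computed 3.1.
- N = 3,360 at 5% (x = 168 exactly), lower limit: printed 4.4, computed 4.29.
- N = 800 at 0%, upper limit: printed 0.4, computed 0.46.

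The printed upper limit of 5.1 for N = 1,680 at 4% can stand: 4% of 1,680 is 67.2 events, which gives 5.05.

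**The case against.** The best defence is that the table is descriptive and its 80% assumption is stated openly. No test or stopping rule uses it, safety is monitored by the safety review team and the DSMB, and the final intervals will use observed denominators. This limits the consequence. It does not reconcile the two sections, because an openly stated assumption still conflicts with a count in the same version that is described as matching study data.

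A reader might also infer that every bound in the panel is too tight. The documents do not support that, for four reasons:

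- They give no version 6 split by group, so the Group 1, 3 and 4 columns are not individually disproved.
- The Safety Subset figure of 600 per vaccine is feasible within 2,000. The subset is drawn at selected sites (Section 9.8), and reactogenicity is collected on the whole Month 6 sentinel cohort of about 120 (Section 2.2.2). Version 6 recipients may therefore be over-represented, and 192 is only a proportional guess.
- Safety is analysed by vaccine actually received (Section 6.2), so the monovalent N can exceed 2,000 if Month 6 recipients from before version 6 are counted.
- The zero lower limits do not change with N, and the misprinted 1.1 makes its interval too wide.

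At the printed one decimal, the full-cohort zero-event limit moves from 0.1 to 0.2.

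**Conclusion.** Wrong as written. Sections 6.3.1 and 6.3.2 conflict, and the N = 6,240 and N = 3,360 columns cannot describe the bivalent vaccine. The four group columns cannot hold together. With about 2,000 bivalent recipients, the full-cohort limits are about 0.18% for zero events, 0.61 to 1.54% at an observed 1%, and 4.1 to 6.0% at 5%.

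This rests on the protocol's own count of about 4,000 split 1:1, and on bivalent vaccine having been given only from version 6 onward. The SAP gives no later count. The proportional figures for the groups and the Safety Subset are illustrations and carry no part of this conclusion. The effect is overstated precision for a primary objective; no hypothesis test, decision rule or conduct of the trial is affected.

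**What to change.** 1. In Section 6.3.2, replace the 80% assumption with the actual numbers dosed at Month 6 under version 6, by vaccine, study group and Safety Subset, and make them agree with Section 6.3.1.
2. Recompute the post-Month 6 panel of Table 6-4 from those counts, with separate columns for mRNA-1273.222 and mRNA-1273. If the monovalent columns include Month 6 recipients from before version 6, state that as-treated N and say that those recipients are outside the randomised comparison.
3. If any existing column is kept, correct its misprint: N = 1,680 at 4%, lower limit 1.1 to 3.1 (leave the upper limit of 5.1); N = 3,360 at 5%, lower limit 4.4 to 4.3; N = 800 at 0%, upper limit 0.4 to 0.5.

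The cost is a table and text edit using counts that the data centre should already hold. The stated bivalent full-cohort precision becomes less favourable.
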